6.1.13. Pre-treatment Bone Marrow Examination

Unilateral bone marrow aspirate smear and a suitable bone marrow biopsy will be performed at baseline (or within 6 weeks prior to entering the study) ONLY to confirm

CR. A pathologist at a central laboratory will evaluate the biopsy and smear. Details regarding collection of bone marrow samples are provided in a separate procedure manual.

6.2. Efficacy

6.2.1. Definition of Response

While subjects will be entering the study in remission, changes in status to disease progression or even from PR to CR will be determined according to the definitions of response in the IWCLL updated NCI-WG guidelines [Hallek, 2008] and documented at visits outlined in the time and events table. For a tabular summary of all criteria of response definition in CLL patients see Appendix 2. The IWCLL updated NCI-WG guidelines should be applied in the context of clinical judgment and determination of disease progression is at the physician's discretion.

6.2.1.1. Complete Remission (CR)

CR requires all of the following criteria as assessed at least 2 months after therapy or at the earliest 2 months after beginning this maintenance protocol (i.e. ofatumumab treatment/observation):

Peripheral blood lymphocytes (evaluated by blood and differential count) below 4×10^9 (4000/ μ L)

Absence of significant lymphadenopathy (e.g. lymph nodes > 1.5 cm diameter).

No hepatomegaly or splenomegaly.

Absence of constitutional symptoms

Blood counts above the following values:

- a. Neutrophils > 1.5×10^9 /L*
- b. Platelets > 100×10^9 /L*
- c. Hemoglobin > 11.0 g/dL (6.8mmol/L)**

*without need for exogenous growth factors

**without red blood cell transfusion or need for exogenous erythropoietin

Bone marrow aspirate and biopsy should be performed at least 2 months after the final treatment and if clinical and laboratory results listed above in Section 6.2.1.1 (items 1 to 5) demonstrated that a CR has been achieved. The marrow sample should be analyzed by flow cytometry to demonstrate that the marrow is free of clonal CLL cells. Cases with residual CLL cells by conventional flow cytometry are defined as PR.

To define a CR, the marrow sample must be at least normocellular for age, with less than 30% of nucleated cells being lymphocytes. Lymphoid nodules should be absent. If lymphoid nodules can be found, immunohistochemistry analysis should be performed to assess if nodules are comprised primarily of T-cells or lymphocytes

other than CLL cells or of CLL cells. If marrow is hypocellular, repeat after 4-6 weeks, provided the blood counts have recovered (as defined in Section 6.2.1.1 item 5). Marrow biopsies should be compared with any pretreatment marrow. In some cases, it is necessary to postpone the marrow biopsy until after all other criteria to define a CR have been satisfied, however, this time interval should not exceed 6 months after treatment.

Subjects who fulfill all the preceding criteria for CR (Section 6.2.1.1 items 1 to 6) but have persistent anemia, thrombocytopenia or neutropenia, apparently unrelated to CLL but related to drug toxicity, should be considered as CR with incomplete bone marrow recovery.

6.2.1.3. Progressive Disease (PD)

PD during or after therapy is characterized by at least one of the following:

1. Lymphadenopathy. Progression of lymphadenopathy, if one of the following is observed:

- Appearance of new lesion such as enlarged lymph nodes (>1.5cm), splenomegaly, hepatomegaly or other organ infiltrates
- An increase by 50% or more in greatest determined diameter of any previous site.

An increase by 50% or more in the previously noted enlargement of the liver or spleen or *de novo* appearance of hepatomegaly or splenomegaly

An increase by 50% or more in the numbers of blood lymphocytes with at least 5000 B-lymphocytes per microliter ($5.0 \times 10^9/L$).

Transformation to a more aggressive histology (e.g. Richter's transformation).

Occurrence of cytopenia (neutropenia, anemia or thrombocytopenia) attributable to CLL

- During therapy: Cytopenias cannot be used to define disease progression
- After treatment: The progression of any cytopenia (unrelated to autoimmune cytopenia), as documented by a decrease of Hb levels by more than 20g/L (2 g/dL) or to less than 100g/L (10g/dL), or by a decrease of platelet counts by more than 50% or to less than $100 \times 10^9/L$ (100,000/ μL), which occurs at least 3 months after treatment, defines disease progression, if the marrow biopsy demonstrates an infiltrate of clonal CLL cells.

Note: Physician's discretion should be used to distinguish between potential infection versus progressive disease base on lymphocyte count. It is acceptable to defer definitive judgment of progressive disease until further evidence is available.

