3.1.3. Treatment Phase

Subjects randomized to treatment arm A will receive ofatumumab whereas subjects randomized to treatment arm B will receive no further treatment (i.e. observation only).

Arm A:

Ofatumumab:

- 300mg IV Week 1 followed by 1000mg IV on Week 2
- 1000mg IV (1 dose every 8 weeks for up to 2 years following the first 1000 mg dose)

OR

Arm B:

- No further treatment (observation and assessments as per arm A)

Disease status assessments to determine subject response or progression will be performed approximately every 8 weeks for up to 2 years for both arms according to NCI Criteria [Hallek, 2008] and will include:

- Physical examination including lymph node examination, spleen and liver measurement, and detection of constitutional symptoms
- Peripheral blood sample evaluation of complete blood count (CBC) and differential (expressed in % and absolutes)

Monitoring and treatment of potential Tumor Lysis Syndrome (TLS) during the first cycle will be performed as per oncology standard of care.

Patient Reported Outcome (PRO) measures (EORTC QLQ-C30, EORTC QLQ-CLL16, EQ-5D) will be administered for completion by subjects at baseline, at each treatment visit beginning with Visit 3, at last visit, and at follow-up visits. A Health Change Questionnaire will be administered for completion by the subjects at all post baseline visits, as per Section 6.5.6.

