4.2. Inclusion Criteria

Subjects eligible for enrollment in the study must meet all of the following criteria:

1. Adults with documented diagnosis of CLL based on the modified IWCLL updated NCI-WG guidelines [Hallek, 2008]
2. At least PR according to the revised 2008 NCI-WG CLL criteria within 3 months of the response assessment after the last dose of 2nd/3rd line treatment
3. The anti-leukemic treatment before study entry should have been for at least 3 months or 3 cycles
4. ECOG Performance Status of 0-2
5. Signed written informed consent prior to performing any study-specific procedures

French subjects: In France, a subject will be eligible for inclusion in this study only if either affiliated to or a beneficiary of a social security category.

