11. APPENDICES

11.1. Appendix 1: Time and Events

Phase	SCREEN	Treatment or Observation (~ every 8 wks after 1 st visit)			Follow-up (every 3 months for 5 years)	WD
		1	2	3-14		
Visit	Screening	1	2	3-14	15-34	
Week	(-6 to -1)	1	2	9-97	109-337	
Month	0	1	1	3-25	28-85	
Visit Window		± 7d	± 3d	± 7d	± 14d	
Administration of Ofatumumab (if assigned to treatment group)		X	X	X		
Informed Consent	X					
Eligibility Criteria	X					
Demographics	X					
Medical History ¹	X					
Height	X					
Body weight	X		X	X	X	X
Physical Exam	X		X	X	X	X
Lymph node evaluation	X		X	X	X	X
Organ Evaluation	X		X	X	X	X
ECOG	X		X	X	X	X
ECG	X					
Adverse Event Assessments		X	X	X	X ¹²	X
Concomitant Medications		X	X	X	X ¹²	X
CT Scan	X			X ²	X ²	X
Bone marrow biopsy	X ³			X ³		
Flow cytometry (MRD)	X ³			X ³	X ³	X ³
Flow cytometry(CD5/CD19)	X			X	X ⁴	X
Prognostic Factors ⁵	X					X
Response Evaluation		X	X	X	X	X
PRO	X			X	X	X
Hematology ⁶	X	X	X	X	X	X
Biochemistry ⁶	X	X	X	X	X	X
Hepatitis ⁷ and Pregnancy Test	X					
Igs	X			X ^{8,9}		
HABA ¹⁰		X		X ^{8,9}	X ⁹	X
Coombs and CH50	X				X	
PK Sampling ¹¹		X	X	X	X	X
Vital Signs	X	X	X	X	X	

1. Medical history to include disease characteristics as defined in Section 6.1.
2. Screening, yearly while on study, at the subject's last treatment visit and upon relapse
3. For subjects in CR ONLY- may be confirmed with bone marrow biopsy/flow cytometry
4. Until B-cell value is within normal levels (See Section 6.3.1.2.)
5. Prognostic Factors as defined in Section 6.3.3
6. See Section 6.3.2
7. Subjects that are HBsAg negative, HBcAb positive and HBV DNA negative may be included but must undergo HBV DNA monitoring as listed in Section 6.3.4
8. At the subject's last treatment visit
9. Every six months. Igs may be assessed during infection per PI. (See Section 6.3.4)
10. HAHA for ofatumumab treatment only-predose, every six months, at last treatment, and 3& 6 months post last ofatumumab dose, regardless of when it occurs.
(See Section 6.3.4)
11. For pharmacokinetic sampling, see Table 5, Section 6.6; + 15 min window for 0.5h post EOI samples is allowed
12. Only SAEs and associated concomitant medications are to be reported from 60 days after the last dose/observation time. (See Section 6.4.8.)

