11.2. Appendix 2: Response Definition Summary

This table is based on the parameters described in Section 6.2.1.

Parameter	CR	PR	PD
Response definition:	All criteria to be met	At least 2 of criteria 1, 2, 3 plus one criteria of 5a-c to be met (minimum duration of 2 months)	At least one criteria to be met
1	Blood lymphocytes <4000/ μ L	\geq 50% decrease from BL	\geq 50% increase over BL (and \geq 5000/ μ L B-cells)
2	Lymphadenopathy ¹ absent (none >1.5cm)	\geq 50% decrease from BL, no increase or new	\geq 50% increase or new (>1.5cm)
3	Hepato/spleno megaly absent	\geq 50% decrease from BL	Increase \geq 50%, or new
4	Constitutional symptoms absent	n/a	n/a
5a	Neutrophils >1500/ μ L	>1500/ μ L or \geq 50% increase over BL	n/a
5b	Platelet count >100,000/uL	>100,000/uL or \geq 50% increase over BL	\geq 50% decrease from B, or to >100,000/uL second. to CLL ²
5c	Hemoglobin >11 g/dL	>11 g/dL or increase \geq 50% over BL	Decrease of >2 g/dL from BL or to <10 g/dL second. to CLL ²
6	Marrow Normocellular, no B-lymphoid nodules, <30% lymphocytes	n/a	n/a
7	other n/a	n/a	CLL- transformation, cytopenia after treatment

1. Sum of the products of multiple lymph nodes

2. Occurrence of cytopenia attributable to CLL at least 3 months after treatment defines disease progression, if the marrow biopsy demonstrates an infiltrate of clonal CLL cells

BL=baseline,

Note: SD is defined as absence of progressive disease (PD) and failure to achieve at least a PR.

Modified from Table 4 IWCLL guidelines [Hallek, 2008]. For complete description and guidance, please refer to Hallek, 2008.

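### Read literally, cytopenia can count as progression on observation but not on ofatumumab for up to about 27 months; the plan does not say which branch covers observation, and no planned analysis would show the effect

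*Protocol*

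**What the plan says.** Protocol 6.2.1.3 lists cytopenia attributable to CLL as one route to progressive disease (PD) and splits it in two. On therapy the route is shut: "During therapy: Cytopenias cannot be used to define disease progression". After treatment it opens. A hemoglobin fall of more than 2 g/dL or to below 10 g/dL, or a platelet fall of more than 50% or to below 100 × 10⁹/L, unrelated to autoimmune cytopenia, "which occurs at least 3 months after treatment, defines disease progression, if the marrow biopsy demonstrates an infiltrate of clonal CLL cells". The Appendix 2 footnote repeats the second branch: "Occurrence of cytopenia attributable to CLL at least 3 months after treatment defines disease progression".

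Under Protocol 3.1.3, Arm A receives "1000mg IV (1 dose every 8 weeks for up to 2 years following the first 1000 mg dose" and Arm B "No further treatment (observation and assessments as per arm A". Entry requires at least PR "within 3 months of the response assessment after the last dose of 2nd/3rd line treatment" (Protocol 4.2).

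Neither 6.2.1.3 nor Appendix 2 says which branch covers Arm B. SAP 9.3 gives the observation arm an on-treatment period from randomization to follow-up entry, but only to assign data to time periods. SAP 9.2.1 states that observation subjects do not receive treatment.

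The primary analysis uses investigator-assessed PD (SAP 11.1), and Protocol 6.2.1 leaves PD to the physician's discretion in an open-label trial.

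**The concern.** Therapy status is the thing that was randomized. A PD criterion that switches on it can give different PFS outcomes to two subjects with the same hemoglobin, platelets and marrow, only because they are in different arms. An event route open on observation and closed on ofatumumab can shift the comparison in one direction only, toward ofatumumab. Protocol 3.2 argues that the open-label design does no harm because the endpoints are objective, but objectivity does not help if the criterion itself differs by arm.

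No planned analysis would show the effect. The three PFS sensitivity analyses in SAP 11.1 change the assessor or the use of CT. The independent review works to the same response criteria. SAP 11.3.2 counts progressions by arm and period, but not by the criterion met. No listed output for the 280-event analysis separates or removes cytopenia-only PD.

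**Working it through.** **1. The plan's own figure.** HR = 28/39.2 = 0.714. Schoenfeld events = 4(1.960 + 0.842)²/(ln 0.714)² = 278; Freedman gives 283; the plan states 280. Power at 280 events for ofatumumab medians of 35, 36.4, 39.2 and 42 months is 0.463, 0.593, 0.804 and 0.924, against 0.47, 0.60, 0.80 and 0.92 stated. Time to 280 events with 478 subjects at 12 per month is 63.4 months (63.5 stated). The design figures reproduce and do not depend on the cytopenia rule.

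**2. When the route is open, read literally.**

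| | Ofatumumab | Observation |
|---|---|---|
| Last treatment | last study dose, up to 2 years in | last induction dose, before randomization |
| Cytopenia can count from | 3 months later: up to 24 + 3 = 27 months | at or soon after randomization, at most 3 months later |
| Early discontinuation | opens 3 months after the last dose | not applicable |

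Twenty-seven months is the outer limit. The last dosing visit in Appendix 1 is at Week 97, which is 96 weeks or about 22 months after Week 1, so about 25 months with the wait.

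**3. How narrow the route is.** Cytopenia-only PD needs attribution to CLL and a biopsy showing clonal CLL. Protocol 6.2.2 ties marrow examination to CR evaluation, and the Appendix 1 footnote reads "For subjects in CR ONLY- may be confirmed with bone marrow biopsy/flow cytometry". The marrow row has no entry for follow-up or withdrawal. CT is required at progression; marrow is not. The event therefore needs an unscheduled biopsy.

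**4. Size, as an upper bound.** The documents give no count of cytopenia-only PD. Assume a share f of the progression hazard is cytopenia-first, the same in both arms, counted on observation and never on ofatumumab. Then HR(observed) = (1 − f) × HR(symmetric).

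| f | HR if no true effect | Interim 0.50 (0.38–0.66) becomes | 280-event 0.55 (0.43–0.70) becomes |
|---|---|---|---|
| 1% | 0.99 | 0.505 (0.384–0.667) | 0.556 (0.434–0.707) |
| 5% | 0.95 | 0.526 (0.400–0.695) | 0.579 (0.453–0.737) |
| 10% | 0.90 | 0.556 (0.422–0.733) | 0.611 (0.478–0.778) |
| 20% | 0.80 | 0.625 (0.475–0.825) | 0.688 (0.537–0.875) |

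**5. Size, with the asymmetry limited to 27 months.** Simulation under no true effect: 478 subjects, 280 events, 2,000 runs per setting. On ofatumumab, a cytopenia-first event before month 27 is deferred to month 27 unless another criterion is met sooner. A false win is rejection in favour of ofatumumab at two-sided 0.0498 (nominal about 2.5%).

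| f | Median 28 months (design): HR, false win | Median 15.2 months (interim, observation arm): HR, false win |
|---|---|---|
| 0 | 0.997, 2.5% | 1.005, 2.3% |
| 5% | 0.982, 4.1% | 0.958, 4.7% |
| 10% | 0.966, 4.3% | 0.931, 9.3% |
| 20% | 0.930, 9.3% | 0.860, 24.4% |

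Simulation error on a 4% rate is √(0.04 × 0.96/2000) = 0.4 percentage points.

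**6. What it would take to change the result.** The interim standard error of ln HR is ln(0.66/0.38)/(2 × 1.96) = 0.141. Two-sided p = 0.001 corresponds to HR = exp(−3.29 × 0.141) = 0.629. On the upper-bound model this needs f = 1 − 0.50/0.629 = about 20.5%. The interim confidence limit reaches 1 at f = 1 − 0.66 = 34%, and the 280-event limit at 1 − 0.70 = 30%.

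**The case against.** The strongest reply is that the asymmetry is an inference. Protocol 3.1.3 assesses Arm B as Arm A, Appendix 1 has one column for treatment or observation, 6.2.1.1 treats the two as parallel, and SAP 9.3 calls the observation phase on-treatment. Sites may have barred cytopenia in both arms during that phase. This stands as a possible reading. It is not a stated rule: none of these places defines PD. Elsewhere the authors name observation alongside treatment when both arms are meant, and the cytopenia branches do not.

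The second reply, that the required biopsy is unscheduled and events may be few or none, also stands.

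A reader might go further and infer that the biopsy condition filters little in PR subjects, from the line "Cases with residual CLL cells by conventional flow cytometry are defined as PR". The documents do not support that. The line downgrades a would-be CR with residual cells on flow cytometry. The PR definition in 6.2.1.2 has no marrow item, and Appendix 2 marks marrow as not applicable for PR. It does not follow that PR subjects generally have an infiltrate on biopsy.

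**Conclusion.** The point holds as a defect in the endpoint definition. Followed literally, the rule treats identical subjects differently by arm, the text does not settle which branch covers observation, and no planned analysis would reveal the consequence.

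A reader might infer that the reported effect is demonstrably overstated. The documents do not show that: f is unknown and could be near zero. They support only the direction of any bias and a conditional range. For f of 5% or 10%, the null HR is about 0.96–0.98 or 0.93–0.97, and the interim HR becomes at most about 0.53 or 0.56. This assumes constant hazards and the same f in both arms. The step-4 figures are upper bounds, because some uncounted cases would soon qualify by another criterion. The step-5 figures ignore early discontinuers, who regain the criterion sooner.

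Nor does the point threaten the conclusion: the interim result would stay below 0.001 until f reached about 20%. What is at stake is the size of the estimate and the clarity of the primary endpoint.

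**What to change.** 1. Reconcile Protocol 6.2.1.3, Appendix 2 and SAP 11.1 so that, for the PFS endpoint, the cytopenia branch is defined by study phase and is the same in both arms. This concerns how the endpoint is derived, not how subjects are managed.
2. Tabulate investigator PD by qualifying criterion, arm and study period. If the cytopenia-only count is near zero, this table closes the question.
3. Add one PFS sensitivity analysis on the 280-event data in which PD based on cytopenia alone is not an event in either arm. Dropping such calls on observation only would be one-sided, since ofatumumab subjects who stop early regain the criterion. Identify these cases positively (hemoglobin or platelet criterion met, no other criterion met), so that discretionary PD calls made for other reasons are kept.
4. State the censoring rule for reclassified subjects, because disease assessments may stop after PD (Protocol 3.1.4), and report how many it affects in each arm.

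Hemoglobin, platelets, lymphocytes, nodes and organs are already required for an adequate assessment (SAP 9.2.12). Transformation and any biopsy result must come from elsewhere in the record.

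The cost is a wording change, one table and one supplementary analysis. Some genuine marrow-failure progressions will be counted later or censored, and the HR may be slightly less favourable. The new HR should be reported beside the as-assessed one, not in its place.

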6.2.2. Bone Marrow Examination

Unilateral bone marrow aspirate smear and a suitable bone marrow biopsy will be performed at baseline (or within 6 weeks prior to entering the study) ONLY as part of the CR evaluation for patients entering or during the study in CR. A pathologist at a central laboratory will evaluate the biopsy and smear. Details regarding collection of bone marrow samples are provided in a separate procedure manual.

Bone marrow examination (aspirate smear and biopsy) to confirm CR, as determined by the clinical and laboratory results listed in Section 6.2.1.1 is required at least 2 months after completion of therapy or at least 2 months of therapy or response while on study. The marrow should be analyzed by flow cytometry to confirm absence of clonal CLL cells. Samples are to be reviewed in conjunction with any prior pathology, as available.

Minimal residual disease assessment will also be performed on bone marrow aspirate obtained after CR (see Section 6.2.3). When possible, the first drop from bone marrow aspirate will be used for MRD measurement.

6.2.3. Minimal Residual Disease (MRD)

For subjects enrolling in the study who are in CR, baseline MRD will be assessed at screening, prior to any treatment visit.

For subjects who improve to a CR while on study, a bone marrow examination will be performed after at least 2 months of therapy or response while on study.

The bone marrow sample if available, and/or peripheral blood sample will be examined by flow cytometry with the following B-CLL MRD panel [Rawston, 2007]:

- CD5/CD19 with CD20/CD38
- CD5/CD19 with CD81/CD22
- CD5/CD19 with CD79b/CD43

In addition CD3/CD19 with CD14/CD45 analysis is performed to allow enumeration of CD19+ cells and contamination assessment and CD5/CD19 with Igλ/Igκ analysis is performed to confirm clonality.

Subjects with negative MRD will receive follow-up MRD assessments of the peripheral blood until MRD analysis becomes positive.

The absence of MRD is defined as less than one B-CLL cell per 10,000 leukocytes.

6.2.4. CT-Scans

According to the IWCLL updated NCI-WG response criteria for CLL [Hallek, 2008], CT-scans are recommended in clinical trials to assess response. This study will prospectively explore the validity of CT scans for a more sensitive detection of disease progression. CT-Scans are required prior to start of therapy. CT scans will be done approximately yearly while on study including at the end of treatment/observation, and/or upon relapse. If a scheduled CT scan indicates disease progression, and the subject will be withdrawn, it is not necessary to repeat a CT scan for a withdrawal visit. The actual CT scan (not just the radiologist report) should be available and performed to the criteria specified in the SPM.

6.3. Laboratory Assessments

All the analyses will be performed by a central laboratory, except for the direct antiglobulin test (Coomb's test) that will be performed locally. A detailed description of the procedures for sampling, handling, storage, and shipment of the laboratory samples and all material such as test tubes and labels is provided in the SPM or by the central laboratory.

The protocol should be followed as closely as possible, but if as per local practice, a blood draw for hematology analysis prior to the visit date is required, it would be acceptable for hematology analysis, but the blood draw can be taken no more than 3 days ahead of the visit date. Blood draws performed by local laboratories (e.g. for quicker pre-dose response assessment) of protocol required lab assessments are acceptable, however, it is important that the sample for the central laboratory analysis is taken at the same time. The local laboratory results of absolute neutrophil count (ANC), platelet count, peripheral blood lymphocytes, and hemoglobin must also be entered into the eCRF, if these results are used to manage a treatment decision. Central laboratory

information will also be entered into the eCRF. Safety assessments, such as hematology not specified in the protocol, are allowed between visits, per investigator discretion and local practice.

